Statistical Design and Power

Data analyses will proceed with the intent-to-treat sample. Initial analyses will compare groups on baseline and demographic variables using chi-square test (for categorical variables) and analysis of variance (for continuous variables). Variables that significantly differ between groups or are theoretically important, such as pain and other (non-opioid) substance use disorder will be used as covariates in multivariate analysis, when appropriate. For end-of-treatment outcomes, analysis will compare groups via chi-square, Kruskal-Wallis test, and analysis of variance (ANOVA) or analysis of covariance (ANCOVA) tests, as appropriate. Evaluation of changes in outcomes through the follow-up period will occur with hierarchical mixed models specified for dichotomous or continuous outcomes (PROC MIXED and PROC GLIMMIX SAS procedures). These analyses allow for intra-subject serial correlation, unequal variance and covariance structures, and unequally spaced assessment intervals. They also account for missing data by using all available data and maximum likelihood estimation of parameters. To use the mixed effect modeling analysis in assessing intervention effect, an interaction term (intervention group by time) will be included together with other covariates (e.g., age, ethnicity, chronic pain, anxiety, trauma history, utilization of psychiatric or medical services). A significant beta coefficient of the interaction term at $p < .05$ level will be used as evidence supporting the intervention effect. Analysis of change scores can analyze variables that cannot be normalized. For all analyses, effect sizes will be estimated, with parametric and non-parametric statistics as appropriate; effect sizes for effects by sex will be estimated. Statistical significance will be at $p < .05$ and analyses will occur via IBM® SPSS® Statistics V21 and SAS 9.4 statistical software package (SAS Institute Inc, Cary, NC).

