Phase 2, RCT. will proceed with the intent-to-treat sample. Initial analyses will compare groups on baseline and demographic variables using chi-square test (for categorical variables) and analysis of variance (for continuous variables). Variables that significantly differ between groups or are theoretically important, such as pain and other (non-opioid) substance use disorder will be used as covariates in multivariate analysis, when appropriate. For end-of-treatment outcomes, analysis will compare groups via chi-square, Kruskal-Wallis test, and analysis of variance (ANOVA) or analysis of covariance (ANCOVA) tests, as appropriate. Evaluation of changes in outcomes through the follow-up period will occur with hierarchical mixed models specified for dichotomous or continuous outcomes. To use the mixed effect modeling analysis in assessing intervention effect, an interaction term (intervention group by time) will be included together with other covariates (e.g., age, ethnicity, chronic pain, anxiety, trauma history, utilization of psychiatric or medical services). A significant beta coefficient of the interaction term at $p < .05$ level will be used as evidence supporting the intervention effect. Analysis of change scores can analyze variables that cannot be normalized.

The Primary Aim 1 is to assess the efficacy of OARS+CM in promoting Suboxone treatment initiation.

The primary outcomes will be the proportion of participants who schedule a Suboxone treatment intake visit, and the proportion of participants who complete the Suboxone intake visit to start outpatient treatment. These outcomes are usually non-normally distributed and will be analyzed accordingly. We will assess the effect of the intervention using generalized linear mixed model, controlling for the dependence of repeated measures and the clustering effects.

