Sample size justification. We use the proportion of participants who complete the Suboxone intake to start treatment as the calculating indicator. Based on the findings from a large randomized clinical trial on MAT treatment for opioid dependence after an acute care visit,¹⁵⁸ we estimate the proportion of patients who will initiate MAT at baseline is about 35%. We hypothesize that OARS will increase the rate by 25% and OARS+CM will increase the rate by 50%. Using G-Power program (proportions procedure) with $\alpha=0.05$, $N=150$ (50 each group), the calculated statistical power is >0.80 for the comparisons between TAU and OARS, TAU and OARS+CM, and OARS and OARS+CM.

Aim 2 is to assess the efficacy of OARS+CM for increasing Suboxone treatment adherence and abstinence outcomes. Main outcomes will be the percentage of opioid-free urine toxicology tests, and the percentage of group/individual therapy sessions attended. Secondary outcomes will be the longest duration of abstinence (LDA) outcome, measured at month 1, month 3 (end of study period) and month 6 (end of follow-up period), and sustained abstinence from Suboxone start through each follow-up. LDA and sustained abstinence will be as a composite of the greatest number of days with consecutive negative urine samples and self-reported no use; a composite of biochemical evidence and subjective report is needed because urine tests are too infrequent in the clinical setting to rigorously determine sustained abstinence based solely on biochemical evidence. Sustained abstinence and LDA are usually non-normally distributed and will be examined accordingly. We will assess the effect of the intervention using linear mixed model, controlling for the dependence of repeated measures and the clustering effects.

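### The SAP's one stated mixed-model rule, a significant group-by-time term, cannot apply to H1's once-only intake outcomes and, as it stands, does not match H2's 6-month comparison

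*SAP*

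**What the plan says.** **General rule.** Both the opening paragraph of the SAP (Statistical Design and Power) and its Phase 2 RCT paragraph say: "Evaluation of changes in outcomes through the follow-up period will occur with hierarchical mixed models specified for dichotomous or continuous outcomes". To assess the intervention in these models, "an interaction term (intervention group by time) will be included together with other covariates", and significance of that coefficient at the p < .05 "level will be used as evidence supporting the intervention effect". Neither paragraph gives the coding of time or the reference visit.

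**Direct group tests.** These are offered for one occasion: "For end-of-treatment outcomes, analysis will compare groups via chi-square, Kruskal-Wallis test", plus ANOVA or ANCOVA. The assessment table in Protocol section 11 puts end of treatment at month 3.

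**H1 (SAP, Primary Aim 1).** The outcomes are the proportions who schedule and who complete a Suboxone intake. The model sentence reads: "We will assess the effect of the intervention using generalized linear mixed model, controlling for the dependence of repeated measures and the clustering effects". The sample size paragraph says: "We use the proportion of participants who complete the Suboxone intake to start treatment as the calculating indicator", and uses the G-Power routine for proportions.

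**H2.** Protocol section 4 hypothesises higher rates of sustained abstinence over the 6 months after the index visit. The SAP's Aim 2 paragraph lists sustained abstinence as a secondary outcome, counted from the start of Suboxone up to each follow-up (months 1, 3 and 6). It describes it, together with longest duration of abstinence, as a count of consecutive days, and assigns a linear mixed model. No deciding term is named in that paragraph.

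**The concern.** A group-by-time coefficient measures whether the difference between arms changes between visits. That is a sensible test of benefit when the outcome is also measured at intake and the arms start level. Urine toxicology and the pain, HIV-risk and trauma scales in the Protocol section 11 table are examples. Neither H1 nor H2 has that structure.

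For H1 there is only one occasion, so the stated rule has nothing to act on and the test of the primary hypothesis is not written down. For H2 there is no intake value. If the arms separate before month 1 and stay apart, the benefit at 6 months is real but the interaction is close to zero. A reader who follows the SAP to the letter could then report no intervention effect.

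**Working it through.** **1. The plan's own figure, for H1.** The SAP claims power above 0.80 at 50 per group and alpha 0.05, from 35% initiation with increases of 25% and 50%. The usual two-proportion formula is

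power = Φ( [ |p2 − p1| − z·√(2·p̄·(1 − p̄)/n) ] / √(p1(1 − p1)/n + p2(1 − p2)/n) ).

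- Increases read as percentage points, two-sided: TAU v OARS (35 v 60%) gives (0.25 − 0.196)/0.0967 = 0.56, so power 0.71. TAU v OARS+CM (35 v 85%) gives above 0.99. OARS v OARS+CM gives 0.81.
- One-sided, the three are 0.81, above 0.99 and 0.89, which reproduces the claim.
- At the current 51 per arm, two-sided, TAU v OARS+CM has power above 0.99 (points) or 0.43 (relative, 35 v 52.5%).

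The relevant fact is the form of the calculation: it is a comparison of two proportions, that is, a plain group contrast.

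**2. H1: can the stated rule be applied?** Each intake outcome gives one record per participant, and the Protocol section 11 table monitors intake completion in one column only. If every record has the same time value t0, the interaction column equals t0 × group. It is collinear with group, so its coefficient cannot be estimated. Without time terms the model is a logistic regression (with a clustering term if kept), and its group coefficient can test H1. The SAP does not say that this coefficient decides.

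**3. H2: what the rule tests.** With linear time at months 1, 3 and 6, the mean is 10/3 and the sum of squared deviations is 49/9 + 1/9 + 64/9 = 12.67. The slope weights are therefore −0.1842, −0.0263 and +0.2105. If the arms differ by g1, g3 and g6, the interaction estimates

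D = −0.1842·g1 − 0.0263·g3 + 0.2105·g6.

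H2 concerns g6 alone. A parallel gap gives D = 0 whatever its size.

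**4. H2 as yes/no: size.** The documents give no abstinence rates, so these are assumptions: month-6 rates of 35 v 60, 30 v 55, 20 v 45, 20 v 40, 10 v 30 and 50 v 75%; 51 per arm; two-sided .05; complete data; relapse that cannot be reversed, with S(t) = S6^((t/6)^k). There were 10,000 simulated trials per setting. The interaction is a t-test on participant slopes (linear scale), and month 6 is the pooled two-proportion test. Repeat runs differ by about 0.01.

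| Pattern | Gap at months 1, 3, 6 for 35 v 60 (points) | D (points per month) | Interaction power, 35 v 60 | Interaction power, all pairs | Month-6 power, all pairs |
|---|---|---|---|---|---|
| Early losses, k = 0.5 | 16.0, 22.1, 25.0 | 1.7 | 0.17 | 0.06-0.30 | 0.60-0.78 |
| Constant, k = 1 | 7.9, 18.3, 25.0 | 3.3 | 0.41 | 0.09-0.54 | 0.60-0.78 |
| Late, k = 2 | 1.5, 11.1, 25.0 | 4.7 | 0.65 | 0.46-0.72 | 0.60-0.78 |
| Very late, k = 4 | 0.0, 3.2, 25.0 | 5.2 | 0.72 | 0.58-0.77 | 0.60-0.78 |

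Two further patterns were set directly, each in two settings:
- Parallel 25-point gap from month 1, (45, 40, 35) v (70, 65, 60)% and (40, 30, 20) v (65, 55, 45)%: interaction 0.05, month 6 0.75-0.79.
- Same rates through month 3, then 35 v 60%, from (90, 75)% or (80, 60)% at months 1 and 3: interaction 0.77-0.84, month 6 about 0.75.

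The sign can also mislead. For 10 v 30% with early losses the gaps are 22.1, 23.1 and 20.0 points, so D = −4.07 − 0.61 + 4.21 = −0.47. The interaction points away from an arm that is 20 points better at month 6.

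**5. H2 as days.** Under the same relapse scenarios, with days abstinent = min(relapse time, t), both tests have power between about 0.51 and 0.81 and are never more than 0.02 apart. If the gap closes by month 6, some power is lost: with (30, 20, 20) v (60, 40, 20)% the interaction has 0.49-0.51 against 0.57.

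**The case against.** **H1 is only loose wording.** Since the interaction cannot be estimated, the group coefficient is the one intervention term left, and the sizing points to it. This largely stands: there is little real choice of term, and no numerical loss for H1 is shown. But no sentence names the deciding test of the primary hypothesis. Treating scheduling and completion as the two repeated measures does not help, because the interaction would then ask whether the effect differs between them.

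**The SAP is not silent on H2.** This stands. The general rule reaches sustained abstinence through the Aim 2 mixed model, so the fault is a mismatch with the hypothesis, not an omission of any rule.

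**The mismatch depends on coding.** This also stands. If a common zero start were the reference visit and time a category, the month-6 interaction would equal the month-6 difference. The SAP states neither the coding nor the reference.

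**The SAP's own definition is in days, where the tests nearly agree.** That is the more natural reading of the Aim 2 paragraph, while Protocol section 4 speaks of rates. Protocol section 10 refers endpoints to grant pages that are not available here, which may settle it. The power loss is therefore conditional.

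**Conclusion.** The point holds as a fault of specification that should be fixed. The group-by-time rule cannot be applied to the intake outcomes. Under linear time or a month-1 reference it answers a different question from H2, and direct group tests are stated for end of treatment only.

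The size applies to H2 alone and rests on assumed rates, complete data and a linear-scale test. If sustained abstinence is yes/no, interaction power is about 0.06-0.30, 0.09-0.54 and 0.46-0.72 under early, constant and late losses and 0.05 for a parallel gap, against 0.60-0.79 at month 6. If it is days, the difference is negligible in these scenarios.

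Three stronger readings are not supported:
- That the trial cannot test H1 or loses power for it. The same model without time terms tests it.
- That the interaction is always the weaker test of H2. It does slightly better when the gap opens only after month 3. Equally, a gap that opens mainly late does not remove the loss, as the k = 2 row shows.
- That having two Aim 1 outcomes inflates the error rate. The SAP does not say that either one alone would suffice.

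**What to change.** **H1.** Delete the repeated-measures wording. State that the group coefficient decides, in a logistic model with one record per participant for completed intake, which is already the sizing outcome. Adjust for the randomisation factors in Protocol section 5 (other substance use disorder, gender/sex, race/ethnicity). Keep the planned clustering term, for example clinic, or say why it is dropped. Report the risk difference with a 95% CI.

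**H2.** State whether sustained abstinence is yes/no or days. Let the month-6 group contrast from the longitudinal mixed model decide, with time as a category. Taking the contrast from that model, rather than from a stand-alone month-6 test, keeps the SAP's stated reason for using it: "They also account for missing data by using all available data and maximum likelihood estimation of parameters". Keep group-by-time as supportive for this outcome.

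**Cost.** SAP text and analysis code only, with no added participants or visits. The time pattern becomes descriptive for H2, and a little power is given up if the gap opens only after month 3 (about 0.75 against 0.77-0.84).

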5. BACKGROUND*

See grant: "RESEARCH STRATEGY" (p.2-4) for details. The Procedures for Phase 2 have been modified from the original submission. Updated Procedures are as follows:

Procedures

Screening, recruitment, eligibility and training procedures are in C.2.1 and the Eligibility criteria document.

Randomization will occur following determination of eligibility using an urn procedure and stratifying on 1) other (than opioid) substance use disorder no/yes, 2) gender/sex, 3) race/ethnicity.

TAU with MyMAT (n = 51). In the acute care setting, the Behavioral Health Service run by Drs. [name] and [name] provides SBIRT for substance use disorders, including OUD. They provide SBIRT as part of TAU, including, when possible, warm handoff contact with outpatient MOUD treatment that includes a scheduled outpatient appointment, optimally within 48 hours of the ED visit. Patients randomized to this group will also receive MyMAT, a mobile application with opioid treatment educational content, as an attention control measure against OARS+CM. TAU outpatient suboxone treatment consists of urine toxicology screening, group/individual therapy, and MOUD prescription continent on drugnegative (except cannabis, which is legal in MA) urine toxicology. Treatment visits are typically, weekly in weeks 1-4 and then taper over time, to every other week in weeks 5-8, and monthly in weeks 9-12 and thereafter. Nonadherence can lead to increased frequency/intensity of therapy and urine toxicology until the patient stabilizes. If increased frequency/intensity is unsuccessful, patients may be referred to detoxification and subsequently re-admitted to outpatient care when appropriate.

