Group A: TAU with MyMAT. For TAU participants, the usual care provided to individuals with OUD at the UMass University and Memorial hospitals will be provided. This typically consists of (1) medical stabilization and treatment, as needed; (2) brief counseling and referral to treatment by a social worker or other behavioral health provider, which includes providing a tailored referral list; and (3) when the patient is interested and treatment facility available, a "warm handoff" comprised of contact with the outpatient provider and transportation directly to the facility or a scheduled intake appointment within 48 hours, when feasible. TAU participants will also receive MyMAT, a mobile application with opioid treatment educational content, as an attention control measure against OARS+CM.

Group B: OARS+CM. Participants assigned to OARS+CM will receive the same treatment as in the TAU condition but with the enhancement of the CM features, described in detail in Section C.2.1, Proof-of-concept testing for usability section.

Table 1: Eligibility criteria						
Inclusion	Exclusion					
→ >= 18 years old	 Persistent altered mental status (not alert, not oriented, psychotic). 					
◆ Presenting for acute care at UMass University and Memorial hospitals, including EDs, inpatient medical units, inpatient behavioral health units, or community acute care partners for opioid addiction related health complaints, including opioid overdose, opioid related medical consequences, opioid intoxication or withdrawal syndromes, and/or seeking help for OUD	Patient declines referral to UMass Bridging MAT Clinic, to CleanSlate Addiction Treatment Center, to SaVida Health, to Eleanor Health, or to Spectrum Health Systems for MOUD.					
 Presence of a current DSM-V opioid use disorder (OUD), mild to severe 	 Not interested or willing to participate in MOUD treatment 					
 Medically appropriate for outpatient MOUD treatment, as judged by the 	 Unwilling to use the OARS+CM app (if assigned) 					
treating clinician and behavioral health consultant or toxicologist working with the patient clinically	 Does not have access to their own smartphone with at least iOS 7.1 or Android 4.2, the minimal technology required to run the app, or not willing to access clinic- dedicated computer to access the program 					

	Currently a UMMS student			
 Treatment provider of patient who 	 Prisoner or currently in state custody or 			

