11. PROCEDURES INVOLVED*

Measures: For Phase 1, the System Usability Scale (SUS) (patients and clinicians), Timeline Followback (TLFB) (patients only), and Addiction Severity Index (ASI) (patients only) will be used and is included in this submission. For Phase 2, The Mini Quiz (MQ), Mini-Usability Acceptability Testing (Mini-UAT) questionnaire, Timeline Followback (TLFB), PROMIS Pain Intensity and Interference Scales (PIIS), HIV Risk Behavioral Scale (HRBS), Post-traumatic Stress Diagnostic Scale for DSM-5 (PDS), Treatment Satisfaction Scale (TSS), and the System Usability Scale (SUS) will be used and are included in this submission.

Assessments/Procedures for Phase 2	Intake	Onboarding	Transition to Suboxone	Week 1 to 12	Month 1	Month 3 / End of Tx	Month 6
Mini Quiz, Patient form, OUD	X						
Mini-UAT, Service Utilization, TLFB	X				Х	Х	Х
PIIS, HRBS, PDS, U-Tox	X				Х	Х	Х
Healthcare Utilization	X						Х
App training, warm hand-off scheduling outpatient Suboxone intake		Х					
Monitor completion of MOUD intake			Х				
MOUD TAU / OARS+CM				Х			
Monitor treatment attendance/u-tox				X			
Treatment satisfaction, SUS*						Х	

^{*}Only for OAR+CM group

Phase 1: Aim 1 (Develop OARSCM): 30 Clinicians (20 user testing, 10 dyads) and 30 Patients

- 1a. After the OARSCM is developed, patients meeting criteria and consenting to participate will be guided through using the mobile application on their personal smartphone. If the participant's smartphone is not available for use to complete the instructed tasks, the participant will be able to use a study-provided iPad.
- 1b. Clinicians not associated with a specific patient participant verbally consenting to participate after reviewing the User Testing Fact Sheet will be guided through using the provider portal using a test account on a study provided computer in a private office.
- 1c. Clinicians working at the UMass Bridge Clinic, at the CleanSlate Addiction Treatment Center at SaVida Health, and at Spectrum Health Systems associated with a patient participant (considered a dyad) verbally consenting to participate after reviewing the Dyad Fact Sheet will receive an in-person or virtual training on the provider portal on a study provided computer in a private office. After the training, the clinician will provide standard MAT treatment to patient participants and use the OARSCM provider portal to track treatment.

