5. Patient will not receive any follow up calls after the hospital visit but will have their use of the OARSCM mobile application and engagement with treatment as tracked by the OARSCM mobile application monitored for 4 weeks. Participation in this study will last about 4 weeks once the patient has started MAT treatment. After these 4 weeks, the participants will be informed that their 4-week participation has now ended and that we appreciate their participation. They will also be informed that new information related to their appointments, appointment attendance, appointment engagement and tox results will not be entered into their OARSCM mobile application profile. However, they will be able to view this DATA that had been previously entered throughout the 4-weeks. They will continue to have access to their OARSCM mobile application account in order to use their unredeemed Spins, Prizes, and eGift cards for a short time. During enrollment, patient participants will be given a handout on how to uninstall the application if they no longer want the application on their smart phone after participation. See grant: "RESEARCH STRATEGY" (p. 8). See grant: "APPENDIX" for screenshot of patient notification that their 4-week participation has now ended and handout of how to uninstall the mobile application.

Phase 2: Aims 1 and 2 (Efficacy of OARSCM): 102 patients randomized to 1 of 2 groups If the patient agrees to participate:

- 1. Participants (acute care patients who meet eligibility criteria and complete consent process, see section 30. Consent Process) will be randomized to either TAU (with MyMAT) or OARS mobile application plus contingency management (OARSCM).
- 2. Participants will complete an interview assessment during their current medical visit. It takes about 20-30 minutes to complete. They will be asked to provide a urine sample. It will not interfere with their care.
- 3. Participants will be provided a warm handoff to a community-based MOUD treatment provider. All participants will be eligible to receive standard MOUD treatment per treatment as usual at the site they are referred to. If they are randomized to OARSCM, they will use the mobile application to track treatment progress and have the potential to earn prizes for engaging with the application throughout treatment.

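### Aim 1 has two primary outcomes, scheduling and completing an intake, at p < .05 with no stated success rule: if either counts, the false-positive risk is about 9% and Aim 1 can be claimed on bookings alone

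*SAP*

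**What the plan says.** The SAP paragraph on Primary Aim 1 (under Phase 2, RCT) uses the plural and puts two outcomes side by side: "The primary outcomes will be the proportion of participants who schedule a Suboxone treatment intake visit, and the proportion of participants who complete" it. The second is to "complete the Suboxone intake visit to start outpatient treatment", so the clause about starting treatment belongs to completion only. Under Statistical Design and Power the level is given once: "Statistical significance will be at $p < .05". The sample size justification rests on one of the two outcomes: "We use the proportion of participants who complete the Suboxone intake to start treatment as the calculating indicator".

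Protocol section 4 gives Aim 1 a single hypothesis, H1, which is about MOUD treatment initiation. Protocol section 10 refers the endpoints to grant pages that were not supplied. The supplied text contains no hierarchy, alpha split, co-primary requirement or other rule for declaring Aim 1 met.

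On how a booking comes about:

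- Usual care offers "when possible, warm handoff contact with outpatient MOUD treatment that includes a scheduled outpatient appointment" (Protocol section 5), or "transportation directly to the facility or a scheduled intake appointment within 48 hours, when feasible" (Protocol section 6, Group A).
- The assessment table in Protocol section 11 has an onboarding row, "App training, warm hand-off scheduling outpatient Suboxone intake", not limited to one arm. The Phase 2 steps in the same section say: "Participants will be provided a warm handoff to a community-based MOUD treatment provider".
- Only OARS+CM pays a guaranteed 5-dollar prize for scheduling (Protocol section 5, Procedures).

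No scheduling rate is given for either arm.

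**The concern.** The two outcomes do not carry the same meaning. Completing the intake is the SAP's marker of starting treatment. Scheduling is a step before it, which staff help with in both arms and which is paid for in one. A difference in bookings without a difference in treatment starts is therefore plausible.

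If either outcome counts, two separate things go wrong. The error rate under no effect rises above 5%. And a real effect on bookings alone could be reported as success on Aim 1, although H1 is about initiation. The second problem is not a matter of alpha: splitting the alpha would not remove it. If instead both outcomes must succeed, power depends on a scheduling rate that the plan never states. The protocol (section 32) intends the data to support a device submission, so the success rule should be unambiguous.

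**Working it through.** **Inputs.** Two primary outcomes (SAP, Primary Aim 1); significance 0.05 (SAP, Statistical Design and Power), taken as two-sided because the SAP does not say; 51 per arm (Protocol sections 4 and 6); control completion 35% and a hypothesised 50% increase with OARS+CM (SAP, Sample size justification). Scheduling rates are my assumption. Completion is taken as nested in scheduling. That is also an assumption, because section 6 allows direct transport without a booking.

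**Step 1: the plan's own figure.** The SAP states power above 0.80 on completion with 50 per group. Of its three comparisons, only TAU v OARS+CM remains in the two-arm trial. The pooled formula is

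power = Φ{[|p1 − p2|√n − 1.96√(2p̄(1 − p̄))] / √(p1(1 − p1) + p2(1 − p2))}.

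- Increase read as percentage points (35 v 85%): 1.00 at n = 50, which agrees with the SAP. At n = 51: (3.571 − 1.358)/0.596 = 3.71, power 0.9999.
- Increase read as relative (35 v 52.5%): 0.42 at n = 50. At n = 51: (1.250 − 1.375)/0.691 = −0.18, power 0.43.

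Both figures concern completion. The plan has none for scheduling.

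**Step 2: either counts, and neither outcome differs.** For two independent tests at exactly 0.05 the error is 1 − 0.95² = 0.0975. Nested outcomes are correlated, with ρ = √[pc(1 − ps) / (ps(1 − pc))]. At ps = 0.70 and pc = 0.35, ρ = √(0.105/0.455) = 0.48, and the bivariate normal error is 0.091.

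Simulation at 51 per arm draws S ~ Bin(51, ps) and C given S ~ Bin(S, 0.35/ps), and applies an uncorrected chi-square test to each outcome. It used 1,000,000 trials per row (400,000 for the first two rows):

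| Scheduling, both arms | P(at least one significant) |
|---|---|
| 36% | 0.060 |
| 40% | 0.074 |
| 50% | 0.090 |
| 60% | 0.093 |
| 70% | 0.093 |
| 80% | 0.094 |
| 90% | 0.095 |
| 95% | 0.092 |
| 98% | 0.064 |
| 100% | 0.051 |

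These count results in either direction. Results favouring OARS+CM make up about half: 0.045 to 0.048 for scheduling of 50 to 95%, against 0.025 for one two-sided test.

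**Steps 3 and 4: scheduling differs.** The first result column is the chance that scheduling is significant for OARS+CM and completion is not, when completion is 35% in both arms. The other two are the chance that both outcomes are significant for OARS+CM, which is the power if both are required.

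| Scheduling, TAU v OARS+CM | Bookings-only win, completion 35 v 35% | Both significant, 35 v 85% | Both significant, 35 v 52.5% |
|---|---|---|---|
| 60 v 90% | 0.93 | 0.96 | 0.45 |
| 70 v 90% | 0.71 | 0.73 | 0.39 |
| 80 v 90% | 0.27 | 0.28 | 0.18 |
| 90 v 95% | 0.14 | 0.14 | 0.09 |

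On the relative reading, completion alone has power of only 0.43 (formula) to 0.46 (simulation), so there the joint rule is not the main limit except near ceiling.

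**The case against.** - **The documents already point to completion.** H1 is about initiation, the sample size uses completion, and nowhere is either outcome said to suffice. This is true, and it is why the 9% is conditional. But basing the sample size on one outcome does not make it the deciding one, and the SAP sentence lists both as equals.
- **The error is two-sided while H1 is directional.** A false result favouring OARS+CM has probability of about 4.5 to 4.8%, not 9%. This stands as a point of level. The comparator is then 2.5%, so the near-doubling is the same.
- **The figure depends on the scheduling rate.** At 40% scheduling it is 7.4%, and near 100% it returns to 5%. This stands. Low scheduling looks unlikely, however, since patients who decline referral or are unwilling to have MOUD treatment are excluded and a warm handoff is part of the procedures.
- **The same features make high scheduling in both arms plausible,** so the bookings-only risk may be nearer 0.14 to 0.27 than 0.71 to 0.93. This is fair. The qualifiers on the usual-care handoff leave room for lower control rates, and the documents do not settle it.
- **The grant pages on endpoints were not supplied** and may hold a rule. That limits the finding to the supplied text. Even so, the rule belongs in the SAP sentence that names the outcomes.

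**Conclusion.** The concern holds. The SAP names two primary outcomes for Aim 1, and the supplied text gives no rule for deciding between them. If either counts, the false-positive risk is about 9% in either direction (0.090 to 0.095 for scheduling of 50 to 95%), lower if scheduling is close to the completion rate or close to 100%. Separately, a true effect on bookings with none on treatment starts could be declared a success, with probability from 0.14 to 0.93 across the scheduling differences examined. These sizes rest on assumed scheduling rates, 35% completion, completion nested in scheduling, and a chi-square test standing in for the planned generalized linear mixed model. That the rule is missing from the supplied text rests on none of them.

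**What to change.** Name completion of the intake visit, already the basis of the sample size, as the single primary outcome for Aim 1, tested two-sided at 0.05, and list scheduling as a secondary or process outcome. Alternatively keep both in fixed sequence: test scheduling at 0.05 only if completion is significant. Either option holds the error at 0.05 and costs no power on completion.

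A Bonferroni split at 0.025 each would also hold the error, and completion would keep power 0.9996 at 35 v 85%. But it would still allow a primary claim on bookings alone, so it is the weaker choice.

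The change is one SAP sentence and the matching outcome listing, made before outcomes are compared by arm. It needs no new data or patients. The one downside is that scheduling alone can no longer support a primary claim.
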